### 7.5. SAE Reporting to KCI®

The SAE collection/reporting period will begin after the Subject has been randomized. SAEs will be reported via the KCI® SAE Report Form. This form should be completed by the Investigator, or designee, and submitted (fax or email) to KCI® within 24 hours of the Investigator becoming aware of the event. The KCI® SAE inbox is available for SAE reporting 24 hours per day and is monitored during normal business hours.

### 7.6. UADE Reporting - Unanticipated Adverse Device Effect (UADE)

A UADE is any SAE on health or safety or any life-threatening problem or death caused by, or associated with, a device, if that effect, problem, or death was not previously

identified in nature, severity, or degree of incidence in the investigational plan or application (including a supplementary plan or application), or any other unanticipated serious problem associated with a device that relates to the rights, safety, or welfare of Subjects.

The Sponsor (KCI®) will immediately conduct an evaluation of the received SAEs to determine whether the event meets the UADE definition. If the event is determined to be a UADE, KCI® will report the results of the evaluation to the United States Food & Drug Administration (FDA) and to participating Investigators.

If KCI® determines that the event presents an unreasonable risk to the study Subjects, it will terminate all clinical studies or parts of studies presenting risk as soon as possible.

## **7.7. Follow-up Period for Ongoing AEs**

Treatment-related AEs (serious and non-serious) that are ongoing at the final study visit will be followed up to 30 days to assess resolution or stabilization. All unrelated AEs will be considered closed at the time the Subject completes participation in the study.

# **8. STATISTICAL CONSIDERATIONS**

## **8.1. Endpoint Definitions for Analysis**

### ***8.1.1. Primary Endpoint***

The primary endpoint is the percent change in the wound bed surface area (cm^2) considered to be clean, healthy, and viable from baseline to Day 6-9 upon the final dressing removal, which is defined as the difference between the final post-baseline assessment value and baseline value. The percent change in the wound bed surface area (cm^2) considered to be clean, healthy, and viable over time will also be explored and defined in a similar fashion as above utilizing values collected at each visit.

### **8.1.2. Secondary Endpoints**

#### *8.1.2.1. Percent change in total wound volume*

This secondary endpoint is the percent change in total wound volume (cm^3) from baseline to Day 6-9 upon the final dressing removal, which is defined as the difference between the final post-baseline assessment value and baseline value, divided by the baseline value and multiplied by 100. The percent change in total wound volume over time will also be explored and defined in a similar fashion as above utilizing values collected at each visit.

#### *8.1.2.2. Percent change in total wound area*

This secondary endpoint is the percent change in total wound area (cm^2) from baseline to Day 6-9 upon the final dressing removal, which is defined as the difference between the final post-baseline assessment value and baseline value, divided by the baseline value and multiplied by 100. The percent change in total wound area over time will also be explored and defined in a similar fashion as above utilizing values collected at each visit.

#### *8.1.2.3. Physician assessment of need for debridement*

This secondary endpoint is the need for debridement of the wound upon completion of study treatment up to Day 6-9, as assessed by the Investigator. For each Subject, there are three possible outcomes for this endpoint:

- “Yes”, which is assigned if the Subject had a need for wound debridement after the completion of treatment.
- “No”, which is assigned if the Subject had no need for wound debridement after the completion of treatment.
- “Incomplete Treatment”, which is assigned if the Subject did not complete assigned treatment for at least six (6) days.

### **8.1.3. Safety Endpoints**

Treatment-emergent adverse events (TEAE) are those that first appear or worsen after the initial application of the assigned study treatment (ie, V.A.C. VERAFL™ Therapy using VFCC or collagenase ointment). Adverse events will be coded using the MedDRA dictionary.

### **8.1.4. Exploratory Endpoints**

Additional exploratory endpoints may be added and will be detailed in the SAP. Definitions regarding exploratory endpoints will also be included in the SAP.

## **8.2. Analysis Sets**

The following analysis sets will be used:

- Safety Analysis Set – The Safety Analysis Set will consist of all consented Subjects who received either VFCC and NPWTi-d or collagenase ointment for any length of time. Subjects will be analyzed as treated.
- Intention-to-treat (ITT) Analysis Set – The ITT Set will consist of all randomized Subjects. Subjects will be analyzed as randomized.
- Modified Intent-to-treat (mITT) – The mITT will consist of all randomized Subjects with the following:
  - i. met all the inclusion criteria and none of the exclusion criteria,
  - ii. has no more than 2/3 of the wound bed surface area considered to be clean, healthy, viable wound bed as determined at the baseline measurement confirmed with 3D images by an independent assessor,
  - iii. received either the V.A.C. VERAFL CLEANSE CHOICE™ Dressing and NPWTi-d or collagenase ointment,
  - iv. had the primary endpoint assessment on Day 6-9.
- Per-Protocol Analysis Set – This set will include Subjects in the mITT who had no disqualifying protocol deviation(s) that would impact the interpretation of the

primary endpoint. The disqualifying protocol deviation(s) for exclusion from this set will be defined and documented in a blinded fashion prior to the final database lock. Subject data will be analyzed in the arm to which they were randomized and treated.

### **8.3. Planned Analysis and Data Summaries**

#### **8.3.1. General Analysis Techniques**

In general, continuous variables will be summarized by providing the number of Subjects with available data (n), the mean, median, standard deviation, minimum, and maximum values. For categorical variables, the number and percentage of Subjects that are in each category will be provided. Unless otherwise specified, the denominator for percentages will be all relevant Subjects in a specified analysis set, including those for whom data are not available, ie, “not reported” or “not available” – those data will generally be considered a separate category and included in the displays of data, with the denominator for percentages including these Subjects. Subjects will be summarized by treatment group and overall.

#### **8.3.2. Subject Disposition**

Summaries of disposition will be tabulated by treatment group. The number and percentage of Subjects in the specified analysis set will be described, as will the number and percentage of Subjects who:

- provided informed consent
- failed screening, and the reason for screen failure
- were randomized and treated
- discontinued early from the study for any reason, along with the reason for discontinuation (if the reason is an AE, the system organ class and preferred term)
- completed the study as planned

Subject disposition also will be described in a flowchart (CONSORT diagram).

### **8.3.3. Demographic and Baseline Characteristics**

Demographic characteristics (eg, age, sex, race, and ethnicity), baseline characteristics, and other disease characteristics will be summarized per the general techniques in Section 8.3.1. Subjects in the mITT, ITT, and/or Per-Protocol Analysis Sets will be summarized by treatment arm and overall.

### **8.3.4. Analysis of Primary Endpoint**

The primary endpoint will be calculated per the definition in Section 8.1.1. Based on the mITT analysis set, the primary endpoint will be summarized by treatment group and overall.

The null and alternative hypotheses for the primary endpoint are:

Null:  $\Delta_{VFCC - Control} = 0$       Alternative:  $\Delta_{VFCC - Control} \neq 0$

where  $\Delta_{VFCC - Control}$  is the difference in the percent change in the wound bed surface area ( $\text{cm}^2$ ) considered to be clean, healthy, and viable between the VFCC and NPWTi-d group and Control group.

Assessments will be taken at multiple visits for each Subject during the study. The primary endpoint will be analyzed using a repeated measures analysis of covariance model (ANCOVA) with treatment arm, visit, wound undermining measurement, clinical site, and treatment by visit (Note: if clinical site or treatment by visit are not statistically significant, then the non-significant term(s) will be removed from the model and the updated model will be re-run). The analysis will be based on the mITT analysis set.

If appropriate, supportive/exploratory analyses of the primary endpoint may include:

- repeat the analysis above on the ITT and Per-Protocol analysis sets
- a two-sample t-test or a Wilcoxon Rank-Sum test without adjusting for wound undermining
- analyses comparing the treatment groups considering covariates (eg, age, body mass index [BMI], race/ethnicity, sex, wound undermining, and co-morbidities) and subsets of the data

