### **8.6. Interim Analysis**

A nonbinding, unblinded interim analysis will be performed when approximately 30 evaluable subjects have had their assessments for the primary endpoint (percent change on wound bed surface area considered to be clean, healthy and viable from baseline to

Day 6-9). The purpose of the interim analysis is to evaluate the need for early stopping due to futility, efficacy, and/or sample size re-calculation.

The primary endpoint will be analyzed as outlined in Section 8.3.4. If the resulting p-value for the primary analysis is less than  $\alpha=0.006$  as determined utilizing the O'Brien-Fleming  $\alpha$ -spending function (O'Brien 1979), the null hypothesis will be rejected, and the study may be stopped for efficacy.

If the null hypothesis could not be rejected, conditional power will be calculated to assess for futility and/or sample size adjustment. If the conditional power is lower than the pre-specified boundary in the interim SAP, the trial may be stopped for futility. If the conditional power is above the futility boundary, the conditional power will be evaluated utilizing methods described in Chen et al (Chen 2004) to determine if a sample size increase is required.

The final analysis will be conducted at  $\alpha=0.048$  to maintain the overall type I error rate at  $\alpha=0.05$  as determined by the O'Brien-Fleming spending function. Details of the interim analysis will be described in the interim SAP before the interim analysis is conducted.

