8. EFFICACY ANALYSIS

8.1. Primary Efficacy Analysis

The primary endpoint is the change in the percent of wound bed surface area (cm^2) considered to be clean, healthy, and viable from baseline to Day 6-9 upon the final dressing removal. The percentage of clean, healthy, and viable tissue (pctCHV) is defined as the sum of percentages of viable Bone/Cartilage/Ligament/Tissue (B/C/L/T), viable fat, viable muscle/fascia, and granulation tissue. The change in percent (ΔpctCHV) of clean, healthy, and viable tissue from baseline to Day 6-9 upon the final dressing removal is defined as:

$$\Delta\text{pctCHV} = \text{pctCHV}_4 - \text{pctCHV}_0$$

where,

pctCHV₀ = percent of clean, healthy, and viable tissue at baseline

pctCHV₄ = percent of clean, healthy, and viable tissue at Day 6-9 upon final dressing removal.

The following hypothesis will be tested:

Null: $\Delta\text{pctCHV}_{\text{VFCC}} - \Delta\text{pctCHV}_{\text{Control}} = 0$
 $\neq 0$

Alternative: $\Delta\text{pctCHV}_{\text{VFCC}} - \Delta\text{pctCHV}_{\text{Control}}$

where $\Delta pctCHV_{VFCC} - \Delta pctCHV_{Control}$ is the difference of the change in percent of wound bed surface area (cm^2) considered to be clean, healthy, and viable between the VFCC with NPWTi-d group and the Control group.

Generalized linear modeling will be used to analyze the primary endpoint with the following fixed effects: clinical site; baseline percent of wound bed surface considered clean, healthy and viable [pctCHV0]; body mass index [BMI]; treatment arm and indicator of baseline wound undermining.

If any of the covariates (except treatment arm and site ID) is not statistically significant at the 0.1 level, then the non-significant term(s) will be removed from the model and the updated model will be re-run. The analysis will be conducted at the α -level determined by the O'Brien-Fleming α -spending function² and observed fraction time.

```
proc mixed data=adeff;
  class trtp siteid undermin;
  model chg=bmi base trtp siteid undermin / ddfm=kr cl;
  lsmeans trtp/ diff cl;
run;
```

The analysis will be conducted at a final alpha level as determined by the O'Brien-Fleming α -spending function². The primary analysis will be based on the mITT analysis set, and the test of the difference of the least square means estimates.

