8.3.2. Repeated Measures Analyses

In addition, a repeated measures analysis of covariance model (ANCOVA) will be applied to analyze the endpoints of percent of wound bed clean/viable/healthy, total wound volume and total wound area. Fixed covariates of clinical site, treatment arm, wound undermining measurement, visit, and treatment by visit. If clinical site or treatment by visit is not statistically significant, then the non-significant term(s) will be removed from the model, and the updated model will be re-run. Covariance structure will be unstructured, AR(1) or TOEFL, selected based on best fit (likelihood ratio tests or based on appropriate fit statistics).

These endpoints will be summarized based on the mITT and the FAS (with NOCB/LOCF imputation) analysis sets.

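### As written, the interim test and conditional power use a model without baseline viable percentage, although the SAP's final model adjusts for it

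*Protocol*

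**What the plan says.** Protocol 8.3.4 defines the primary analysis as a repeated-measures ANCOVA "with treatment arm, visit, wound undermining measurement, clinical site, and treatment by visit". Site and the treatment-by-visit term may be dropped if not significant. No baseline value of the outcome is listed.

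Protocol 8.6 plans one unblinded, nonbinding look "when approximately 30 evaluable subjects have had their assessments for the primary endpoint" and says "The primary endpoint will be analyzed as outlined in Section 8.3.4". Efficacy is declared if the p-value is below 0.006. Otherwise conditional power is used for futility or a sample-size increase. The final test is at 0.048. The futility boundary and other details are left to an interim SAP.

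SAP 8.1 replaces the primary model with a Day 6-9 model. It contains site, BMI, arm, an undermining indicator and "baseline percent of wound bed surface considered clean, healthy and viable [pctCHV0" (the SAP's name for the baseline value). Covariates other than arm and site are removed if not significant at 0.1.

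SAP 8.3.2, under Exploratory Analysis, carries over the protocol's list: "Fixed covariates of clinical site, treatment arm, wound undermining measurement, visit, and treatment by visit".

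SAP 6.1 does not repeat the assignment to Protocol 8.3.4. It refers interim details to a separate interim SAP, and the SAP revision history mentions changes to the interim plan. That document was not supplied.

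**The concern.** Eligibility allows a baseline viable percentage anywhere from 0 to 2/3, and the outcome cannot exceed 100%. A wound at 60% can gain at most 40 points; a wound at 10% can gain 90. Change is therefore expected to correlate negatively with baseline. A model without baseline leaves that variation in the error term.

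Two things are at stake. First, the interim standard error would be larger than it needs to be, so a real effect is less likely to cross 0.006. Second, conditional power would be computed from one model while projecting a final test that uses another. The baseline image is already taken and read (Protocol 4.10 and 4.14), so the information costs nothing to collect.

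**Working it through.** **Inputs.** Difference 40 - 20 = 20, SD 22 and 23 evaluable per group for about 80% power (Protocol 8.4.1). About 30 evaluable at the interim, so 15 per arm; interim alpha 0.006; final alpha 0.048 (Protocol 8.6). The alternative is two-sided (Protocol 8.3.4). I read the 20, 40 and 22 as percentage points, in line with the SAP endpoint. Assumption: r, the correlation of change with baseline, is not in the documents and is varied.

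**The plan's own figures.** For the Wilcoxon test under a normal shift, P(X<Y) = Φ(20/(22√2)) = 0.740. Then n = (1.960 + 0.842)² / [6 × (0.740 - 0.5)²] = 22.7, so 23 per group, with power 0.804 at 23. This reproduces. The interim level also reproduces at half information: 2 - 2Φ(1.96/√0.5) = 0.0056, which rounds to 0.006.

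**Interim power.** Adjusting for baseline multiplies the SD of change by √(1 - r²). The noncentrality is 20 / (22√(1 - r²) × √(2/15)). Power comes from the noncentral t at two-sided 0.006, with 28 degrees of freedom unadjusted and 27 adjusted. The last column leaves 14 residual degrees of freedom (28 less 14 for about 15 sites).

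| Assumed abs(r) | Residual SD | Noncentrality | Power, no site terms | Power, 14 residual df |
|---|---|---|---|---|
| 0 (no baseline term) | 22.0 | 2.49 | 34% | 28% |
| 0.2 | 21.6 | 2.54 | 35% | 29% |
| 0.33 | 20.8 | 2.64 | 38% | 32% |
| 0.4 | 20.2 | 2.72 | 41% | 35% |
| 0.5 | 19.1 | 2.87 | 47% | 40% |
| 0.6 | 17.6 | 3.11 | 56% | 48% |

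Charging the covariate one more degree of freedom in the last column gives 31% to 47% over 0.33 to 0.6. These are two-sample calculations at Day 6-9. They do not model the earlier visits or any variance explained by site.

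**Conditional power.** Under the current trend, CP = Φ((Z/√t - 1.977)/√(1 - t)), where 1.977 is the critical value for 0.048. At the expected unadjusted Z of 2.49, CP is 0.985 at t = 30/60 and 0.97 at t = 30/46. Trial-to-trial variation matters more, so it was simulated (20,000 trials per setting, t = 30/46). Equal variances at baseline and follow-up were assumed, so abs(r) = √((1 - ρ)/2). Baseline-to-follow-up correlations ρ of 0.3, 0.5 and 0.7 then give abs(r) of 0.59, 0.50 and 0.39.

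| True difference | Mean CP, no baseline | Mean CP, with baseline (ρ = 0.3, 0.5, 0.7) | Share of trials with the unadjusted CP lower |
|---|---|---|---|
| 20 | 0.77 | 0.88, 0.85, 0.81 | 62-79% |
| 10 | 0.36-0.37 | 0.46, 0.42, 0.39 | 57-67% |
| 0 | 0.07 | 0.07 | about 50% |
| -10 | 0.005 | 0.003-0.005 | 34-44% |

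**Chance imbalance.** If baseline were uniform on 0 to 66.7% (assumed), its SD would be 66.7/√12 = 19.3. The standard error of the between-arm difference at 15 per arm is then 19.3 × √(2/15) = 7.0 points. With an assumed slope of -0.5, an imbalance of one standard error moves the unadjusted estimate by 3.5 points, against a design difference of 20.

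**The case against.** The strongest objection is that the model actually used at the look is unknown. SAP 6.1 defers to an interim SAP that was not supplied, and the revision history says the interim plan changed. This stands and makes the interim part conditional. Protocol 8.6 is nevertheless the only interim model in the supplied documents, and the revision history does not say that the interim follows SAP 8.1.

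The following stronger readings are tempting but not supported:

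- *The look is underpowered because of this omission.* A 0.006 boundary at about 30 subjects is meant to be hard to cross, and the 80% target belongs to 23 per group. Most of the low interim power is by design. The gain from baseline is about 2 points or less if abs(r) is 0.2 or smaller.
- *Conditional power is understated, so a needless futility stop is likely.* It is lower on average when VFCC truly works, but not under no effect and not in every trial. The futility boundary is not given and the look is nonbinding, so no such stop can be shown.
- *The comparison is biased or type I error is inflated.* In a randomized comparison the omission costs precision. Nothing here shows bias or inflation.
- *The final analysis loses power too.* SAP 8.1 already includes baseline, subject to its 0.1 retention rule.

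SAP 8.3.2 drives no stopping decision or primary claim. It names levels as its endpoints, whereas SAP 4.1.3 names changes. If the baseline visit is one of the responses, baseline is partly handled; the text does not settle this.

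**Conclusion.** The point holds in a limited form. On the supplied text, the interim test and its conditional power use a model without the measured baseline, while the final model has it. The two do not match, and precision is lost if change depends on baseline. At the design effect, interim power is about 34% without baseline against 38% to 56% with it for abs(r) of 0.33 to 0.6. With site degrees of freedom charged, it is about 28% against 32% to 48%. These figures rest on assumed correlations and a two-sample approximation. The interim part falls away if the interim SAP already adjusts for pctCHV0; the exploratory omission in SAP 8.3.2 would remain. This is a minor point: a low-cost improvement, not a flaw that threatens the trial's conclusion.

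**What to change.** State in Protocol 8.6 or the interim SAP that the interim test and conditional power use the SAP 8.1 model, with baseline pctCHV kept regardless of its p-value. Apply the same retention at the final analysis; otherwise the 0.1 rule could drop baseline at one analysis and keep it at the other. Adding baseline to the Protocol 8.3.4 model instead would still leave the interim and final models different.

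In SAP 8.3.2, add each outcome's own baseline (pctCHV0, baseline volume, baseline area) with a baseline-by-visit term, and use only post-baseline visits as responses.

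The cost is a sentence in each place, one covariate in the code and a few degrees of freedom, with no new data. One consequence should be accepted knowingly: SAP 8.1 always keeps site, whereas Protocol 8.3.4 may drop it. If site would have been dropped, the like-for-unlike comparison is 34% against 32%, 35%, 40% and 48% at abs(r) of 0.33, 0.4, 0.5 and 0.6. At the weaker correlations the benefit is then consistency with the final test and not power.

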## **8.7. Statistical Analysis Plan and Changes in Analyses**

A separate SAP containing full details of the statistical analysis and execution will be finalized prior to the study database lock and the final analysis. Any changes from planned analyses in the study protocol or from the SAP will be noted in the Clinical Study Report (CSR).

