1. INTRODUCTION

The purpose of this Statistical Analysis Plan (SAP) for the EM# 05-014019 clinical investigation plan or CIP (formerly known as KCI.CLEANSE.CHOICE.2017.02) is to outline the analyses planned to support the generation and completion of the Clinical Study Report (CSR). This SAP has been written in accordance with the clinical protocol (Hydromechanical Cleansing With V.A.C. VERAFL0 CLEANSE CHOICE™ Dressing and NPWTi-d vs. Collagenase Ointment in the Management of Full-thickness Wounds (Accelerate Trial), Version 5.0, 13 February 2020) and relevant data collection documents.

This SAP adheres to the requirements and guidelines identified by the U.S. Food and Drug Administration (FDA), European Medicines Agency (EMA), International Conference on Harmonization (ICH) of Technical Requirements for Registration of Pharmaceuticals for Human Use: Guidance on Statistical Principles in Clinical Trials.

The planned analyses identified in this SAP may be included in clinical study reports (CSRs), regulatory submissions, or future manuscripts. Post hoc exploratory analyses not defined in this SAP may be performed to further examine study data. Any post-hoc or unplanned exploratory analysis will be identified as such. This document will be endorsed prior to database lock. Changes made to the SAP before final database lock will be described in the document history. The SAP will not be amended after the final database lock. Deviations from planned analyses, including additional exploratory analyses after database lock, will be noted in the CSR.

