3.4. Blinding

This is an open-label study so blinding of protocol-assigned product use at the clinical sites could not occur.

Prior to the planned interim analysis and prior to the finalization of the interim and final SAPs, any programming of the raw data was stripped of the actual treatment assignment and a dummy treatment assignment used instead. This ensured blinding of interim results during SAP and program development.

The independent assessor is blinded to the treatment assignment when examining the wound images for area, volume and tissue typing.

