6.1. Interim Analysis

A non-binding, unblinded interim analysis will be performed when approximately 30 evaluable Subjects have had their assessments for the primary endpoint (percent change on wound bed surface area considered to be clean, healthy, and viable from baseline to Day 6-9). The purpose of the interim analysis is to evaluate the need for early stopping due to futility, efficacy, and/or sample size re-estimation.

Details of the planned analyses to occur at interim are outlined in the interim Statistical Analysis Plan (SAP) document: CLIN-PROT-SAP-05-813629.

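### Protocol 8.3.4's rule for dropping treatment-by-visit can turn the Day 6-9 test into a Days 2-9 average, and Protocol 8.6 still sends the interim look to that model

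*Protocol*

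**What the plan says.** **Endpoint.** Protocol 8.1.1 measures the endpoint from baseline to Day 6-9, "which is defined as the difference between the final post-baseline assessment value and baseline value". Profiles over time are only to be explored.

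**Protocol model.** Protocol 8.3.4 starts from that definition and then fits a repeated-measures ANCOVA with arm, visit, undermining, site and treatment-by-visit. The post-baseline visits are Day 2-3, Day 4-6 and Day 6-9. A note adds that "if clinical site or treatment by visit are not statistically significant, then the non-significant term(s) will be removed from the model". It gives no significance level.

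**Interim.** At about 30 evaluable subjects, Protocol 8.6 says: "The primary endpoint will be analyzed as outlined in Section 8.3.4". The p-value is compared with 0.006. If the boundary is not crossed, conditional power guides futility and any sample size increase. The final level is 0.048. The same section adds: "Details of the interim analysis will be described in the interim SAP before the interim analysis is conducted". SAP 6.1 likewise says: "Details of the planned analyses to occur at interim are outlined in the interim Statistical Analysis Plan (SAP) document". That document is not among those supplied.

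**Final.** SAP 8.1 models only the baseline-to-Day 6-9 change, on site, baseline percentage, BMI, arm and undermining. It has no visit term. The protocol's model survives in SAP 8.3.2 as exploratory, with the same removal rule.

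**Record of the change.** SAP Section 1 states: "This SAP has been written in accordance with the clinical protocol". SAP Section 10 does not mention the new primary model. SAP Section 12 presents repeated measures as an added exploratory analysis, and its entry for Section 8.1 covers only a proportional odds option.

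**The concern.** A model with visit but no treatment-by-visit term has one arm coefficient for all post-baseline visits. It answers whether the arms differ on average over Days 2-9, not whether they differ at Day 6-9. The two agree in general only if the effect is the same at every visit. With about 15 subjects per arm, a non-significant interaction is weak evidence of that.

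An efficacy look should test the quantity that the final analysis tests. If the interim follows the protocol text, the estimate is pulled below the Day 6-9 effect when benefit builds and above it when benefit fades. The same estimate feeds three decisions: efficacy stopping, futility and sample size.

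In SAP 8.3.2 the rule works against its own purpose. SAP 4.1.3 wants the rate of change and the differences at each visit, and a model without treatment-by-visit cannot show how the arm difference varies over visits.

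**Working it through.** **1. The plan's own figure.** Inputs from Protocol 8.4.1: difference 40 − 20 = 20, SD 22, Wilcoxon test, about 80% power. Noether's formula with P(X<Y) = Φ(20/(22√2)) = 0.7398 gives n per group = (1.96 + 0.84)² / (2 × 12 × 0.25 × 0.2398²) = 22.7, so 23. This reproduces. The calculation uses one value per subject, so it fits a Day 6-9 comparison rather than a visit average.

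**2. What removal does.** The arm coefficient becomes Σ w_v δ_v, where δ_v is the arm difference at visit v. The weights are 1/3 each under compound symmetry (CS) and 0.43/0.13/0.43 under AR(1) with correlation 0.7.

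**3. Assumptions.** The documents give no trajectories, within-subject correlations or removal level. I take 15 per arm (half of about 30), SD 22 at every visit (the protocol gives 22 for the primary endpoint only), and correlation CS 0.5, CS 0.7 or AR(1) 0.7. The removal level is 0.05, with 0.1 as an alternative because SAP 8.1 uses it for covariates. Two illustrative patterns over the three visits are *building* 6.7/13.3/20 and *fading* 20/20/10.

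**4. Chance of removal.** The interaction test is F with 2 and 27 df. Under CS its noncentrality is λ = (15/2) Σ(δ_v − δ̄)² / (22²(1 − ρ)). For the building effect, Σ(δ_v − δ̄)² = 6.67² + 0 + 6.67² = 88.9. So λ = 666.7/242 = 2.75 at ρ = 0.5 and 666.7/145.2 = 4.59 at ρ = 0.7. Power is 27% and 43%, so the term is removed in about 73% and 58% of trials.

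**5. Benchmark: Day 6-9 t test alone at 0.006.** Noncentrality is 20/(22√(2/15)) = 2.49 with critical value 2.97 (28 df), giving 34%. For a Day 6-9 difference of 10, noncentrality is 1.24, giving 6%.

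**6. Whole rule, 40,000 simulated trials per cell, removal level 0.05.** If the term is removed, the mean over visits is tested; if kept, the Day 6-9 difference. Triples are CS 0.5 / CS 0.7 / AR(1) 0.7.

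| True effect | Term removed, % | Simple visit average | p < 0.006 under the rule, % | Day 6-9 test alone, % |
|---|---|---|---|---|
| Building 6.7/13.3/20 | 73/58/74 | (6.7+13.3+20)/3 = 13.3 | 29/28/27 | 34 |
| Fading 20/20/10 | 79/67/74 | (20+20+10)/3 = 16.7 | 28/19/22 | 6 |
| Constant 20 | 95/95/95 | 20 | 53/44/46 | 34 |
| None | 95/95/95 | 0 | 0.6-0.8 | 0.6 |

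For the building effect the mean estimate over all trials, whether the term is kept or removed, is 16.2/17.2/16.2 instead of 20.

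**7. Sensitivity.**
- Removal level 0.1: the building mean is 17.3/18.1/17.2, with crossing 32/31/30%. Fading crosses in 24/17/19%.
- GLS weights instead of the simple mean, removal level 0.05: over all versions, building crosses in 26-32% and fading in 17-31%.
- SDs of 12/17/22 over the visits: building crosses in 35-40% against about 34%, a gain instead of a loss. Fading rises to 35-52%.
- A milder build, 15/18/20: crossing is 34-43% against 34%, with a mean estimate of about 18.

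**8. Overall error with no effect at any visit.** With two-sided levels 0.006 and 0.048, overall alpha is 0.0504 if the two statistics correlate at 0.71 and 0.0522 at 0.5. It is at most 0.006 + 0.048 = 0.054. Taking the 0.8% upper figure for the whole rule at the interim, the bound is 0.008 + 0.048 = 0.056.

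Site, undermining and baseline were not modelled.

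**The case against.** **The interim SAP may settle it.** Both documents defer interim detail to it. SAP Section 12 says the interim alpha was taken out of the SAP to document changes to the interim plan better, so that plan had moved on. A reader might infer that the interim did test an average. Nothing supplied shows this; only the protocol text points that way. This stands, and it makes the interim half of the point conditional.

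**When the term is kept, there is little ambiguity.** Protocol 8.3.4 refers back to the 8.1.1 definition, so a Day 6-9 contrast is the natural reading. The problem lies in the removal case only.

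**Pooling visits can help.** If the effect is constant, the average is unbiased and more powerful. For a building effect, the direction of the change in crossing depends on the assumed SDs and trajectory. A reader might infer that power is lost; the calculations do not support that as a general statement. The clear distortion is for a fading effect, which the documents neither support nor rule out.

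**The harm is bounded.** Stopping is nonbinding and SAP 8.1 governs the final test. A reader might infer inflated type I error or a biased final result. With no effect at any visit the error is near nominal, and the final model has no visit term to average over.

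**The switch of model is in plain view.** SAP 8.1 prints its code, and SAP 8.3.2 is labelled exploratory. SAP Section 12 records changes since SAP V1.0, so the switch may be older, and Protocol 8.7 sends changes to the study report. A reader might infer concealment; the documents do not support that. What remains is that SAP Section 10 lists a lesser departure, on a secondary endpoint's supportive analyses, and omits this one.

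**Conclusion.** The removal rule in Protocol 8.3.4 does not fit the Day 6-9 endpoint, and Protocol 8.6 still routes the interim efficacy test and conditional power through it. On the protocol text the interim and final looks can therefore address different quantities. Whether they do depends on the interim SAP.

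The size rests on assumed trajectories, correlations, removal level and equal SDs of 22. At removal level 0.05, a building effect is attenuated to about 16-17 instead of 20, with crossing possibly lower or higher. A fading effect crosses in about 19-28% against 6%. A constant effect is estimated without bias.

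The same rule in SAP 8.3.2 is at odds with SAP 4.1.3, whatever the interim SAP says. The missing SAP Section 10 entry is a minor transparency point that changes no result.

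Severity: should-fix if the interim SAP follows Protocol 8.3.4 and the look is still ahead; otherwise minor.

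**What to change.** 1. Check the interim SAP. In Protocol 8.3.4 and 8.6, and in the interim SAP if it follows them and the look is still ahead, delete the removal rule for treatment-by-visit. State that both looks test the Day 6-9 contrast, preferably with the SAP 8.1 model. SAP 3.4 uses the past tense ("any programming of the raw data was stripped of the actual treatment assignment") while SAP 6.1 uses the future, so the status of the interim is not clear from the text. If it has been run, report which model was used and change nothing retrospectively.
2. In SAP 8.3.2 keep treatment-by-visit and report visit-specific contrasts, with Day 6-9 named as the one that matches the primary endpoint.
3. In SAP Section 10, record that SAP 8.1 replaced the Protocol 8.3.4 model and that the latter became exploratory, with the reason.

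**Cost.** No new data are needed, but the protocol wording change goes to the IRBs under Protocol 11.2. If the effect is truly constant over visits, interim power is given up: about 34% for an unadjusted Day 6-9 test against 44-54% for the visit average at SD 22. These are not SAP 8.1 figures. That model gains from baseline adjustment and loses degrees of freedom because site always stays in. At an assumed baseline-change correlation of 0.3-0.6, its interim power is about 38-56% with 27 residual df, or 27-42% with 10 df if many sites contribute.
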